8. HYPOTHESIS TESTING METHODS AND MULTIPLICITY CONTROL

8.1. Hypotheses Testing Methods

The statistical hypothesis specified in Section 1.2 will be tested on the selected secondary endpoints at a 2-sided 5% significance level. The study will be declared positive if at least the null hypothesis for the primary efficacy endpoint for REGN5713-5714-5715 versus placebo is rejected.

The hypothesis for other endpoints will be performed using the same procedure and testing method as above.

8.2. Multiplicity Control

The study is powered on the comparison of the primary endpoint between REGN5713-5714-5715 and placebo for Part A of the study with 2-sided alpha level of 0.05.

A hierarchical procedure will be used to control overall Type-1 error rate at 0.05 for the primary endpoint, TNSS (2-6 hours) in birch challenge EEU at day 29 and change from pre-treatment baseline in titrated SPT mean wheal diameter at day 29 in Part A, for testing multiple comparison groups. Each hypothesis will be formally tested only if the preceding one is significant at the 2-sided 0.05 significance level. The hierarchical testing order is shown as below:

- 1. The mean of Total Nasal Symptom Score [TNSS (2 to 6 hours)] during a birch allergen EEU challenge at day 29, in subjects who receive REGN5713-5714-5715 versus placebo
- 2. The percent change from pre-treatment baseline in birch allergen titrated SPT mean wheal diameter AUC at day 29 in subjects who receive REGN5713-5714-5715 versus placebo
- 3. The percent change from pre-treatment baseline in birch allergen titrated SPT mean wheal diameter AUC at day 29 in subjects who receive REGN5713-5715 versus placebo
- 4. The mean of Total Nasal Symptom Score [TNSS (2 to 6 hours)] during a birch allergen EEU challenge at day 29, in subjects who receive REGN5713-5715 versus placebo
- 5. The percent change from pre-treatment baseline in birch allergen titrated SPT mean wheal diameter AUC at day 29 in subjects who receive REGN5715 versus placebo
- 6. The mean of Total Nasal Symptom Score [TNSS (2 to 6 hours)] during a birch allergen EEU challenge at day 29, in subjects who receive REGN5715 versus placebo

9. SUMMARY OF EXPOSURE DATA

9.1. Investigation Study Drug Exposure and Compliance

Part A observation duration:

The number (%) of subjects with observation periods will be presented by specific time periods. The time periods of interest are specified as: ≥ 1 day, ≥ 29 days, ≥ 36 days, ≥ 57 days, ≥ 85 days in Part A and before the 2^{nd} dose.

Part B observation duration:

The time periods of interest are specified as: days during BPS in Part B and after the 2nd dose.

The summary of exposure to study drug will include the duration of exposure in Part A and Part B and the number of study drug administered in each of the two doses, given as 3 injections sequentially on one day for each dose. Duration of exposure will be summarized for each treatment group using the number of participants, mean, SD, minimum, median, Q1, Q3, and maximum.

Treatment compliance is not applicable since the subject will only have two treatment administrations in the study.

9.2. **Duration of Follow-up**

There are two study follow-up periods. The first follow up period is after the last out-of-season EEU exposures until visit 10, where applicable, and the second one is after the end of the BPS until EOS.

9.3. Prior and Concomitant Medications

Medications will be recorded from the day of informed consent until the end-of-study (EOS) visit and will be coded using WHO Drug Dictionary (WHODD). The prior and concomitant medications are defined as below:

Prior medications: medications taken, prior to administration of the first dose of study drug.

Concomitant medications (CMs) for the whole study: medications taken following the first dose of study drug through the EOS visit. The number and proportion of subjects taking prior medications will be summarized by treatment group, as well as the number and proportion taking concomitant medications during the pretreatment period, on-treatment as defined in Section 10.1 based on the FAS.

Prohibited Medications

The prohibited medications will not be analyzed in an independent section but will be included in the prior and concomitant medications.

The number and proportion of subjects performing prior medication will be summarized by treatment group, as well as the number and proportion performing concomitant procedures during the pre-treatment period, on-treatment as defined in Section 10.1 based on the FAS. Similar tables will be provided for the number and proportion of subjects taking prohibited procedures. Each table will be sorted by decreasing frequency of Anatomical Therapeutic Chemical (ATC) level 2

and ATC level 4 based on the overall incidence. Subjects will be counted only once for each medication class (ATC levels 2 and 4) linked to the medication.

Rescue Medications

Participants will be provided with the following allergy-relieving rescue medications (or appropriate in-class equivalent, after agreement with sponsor) to treat allergic symptoms as needed during the study:

- 1. oral desloratadine 5 mg (second generation antihistamine)
- 2. topical olopatadine 1 mg/mL (antihistamine eye drops)
- 3. topical mometasone furoate 50 µg/dose (INCS)

During the screening baseline period and post visit 10 through the end of the study, participants will be asked to record their daily rescue medication use using an e-diary, including the name and amount of these pre-specified medications.

9.4. Prior and Concurrent Procedures

Procedures will be recorded from the day of informed consent until the end-of-study (EOS) visit and all procedures will be coded to a "Preferred Term (PT)" and associated primary "System Organ Class (SOC)" according to the Medical Dictionary for Regulatory Activities (MedDRA). The prior and concomitant procedures are defined as below:

Prior procedures: procedures performed, prior to administration of the first dose of study drug.

Concomitant procedures (CPs) for the whole study: procedures performed following the dose of study drug through the EOS visit.

Number and proportion of participants taking prior/concomitant procedures will be summarized for study total based on the SAF, sorted by decreasing frequency of SOC and PT based on the overall incidence. Participants will be counted only once for each SOC and PT linked to the procedure. Number of participants receiving prior immunotherapy (Subcutaneous Immunotherapy (SCIT), Sublingual Immunotherapy (SLIT)) will be summarized separately.

10. **ANALYSIS OF SAFETY DATA**

The analysis of safety will be performed on the SAF, as defined in Section Section 3.4. The safety analysis will be based on the reported AEs and other safety information (vital signs, physical examination and clinical laboratory parameters).

Date: May 31, 2023

Thresholds for treatment-emergent Potential Clinically Significant Values (PCSV) in laboratory variables are defined in Section 14.3. Treatment-emergent PCSV is any PCSV that developed or worsened in severity compared to the baseline during the on-treatment period which also includes the follow-up period. The baseline when determining treatment-emergent PCSV refers to the baseline value of the study.

The summary of safety results will be presented for each treatment group. The time interval to detect any event or abnormality is during on-treatment period as defined in Section 10.1.

In addition, the summary of safety results (including TEAEs, clinical laboratory, vital signs, and physical examination) will be performed for subjects who were impacted by COVID-19 pandemic and not impacted by COVID-19 pandemic in each study part, respectively if deemed appropriate. The summary will be performed for pre-, during, and post-COVID-19 periods for participants impacted by COVID-19, if deemed appropriate.

10.1. **Adverse Events**

Adverse events (AEs) and serious adverse events (SAEs) as defined in ther study protocol (Section 9.2.1 and Section 9.2.2) will be collected from the time of informed consent signature and then at each visit until the end of the study.

For safety variables, following observation periods are defined:

- The pre-treatment period is defined as the time from signing the ICF but before receiving the first administration of study drug.
- The on-treatment period in study is defined as the first dose date to the end of study (visit 15).

Treatment-emergent adverse events are defined as those that are not present prior to randomization or represent the exacerbation of a pre-existing condition during the on-treatment period (which includes the follow-up period after the end of the local BPS).

All new or worsening AEs occurring between signing of the ICF and the end of the study will be recorded and coded using the Medical Dictionary for Regulatory Activities (MedDRA).

AEs will be summarized with incidence tables for Part A and Part B separately. AE incidence tables will present the number (n) and percentage (%) of participants experiencing an AE within each treatment arm, sorted by decreasing frequency of SOC and PT in the 3-mAb (REGN-5713-5714-5715) treatment arm. Multiple occurrences of the same event in a patient will only be counted once in the summary. For tables showing AE severity, for instances where a patient has multiple occurrences of the same PT or SOC, only the worst severity will be counted in the summary.

The following AE summaries will be presented for TEAEs:

- Overview of TEAEs
- TEAEs by Primary SOC and PT
- TEAEs by PT
- TEAEs by Primary SOC, HLT and PT
- TEAEs by Primary SOC, PT, and Severity
- TEAEs Related to Study Drug by Primary SOC and PT
- Treatment-emergent AESIs by Primary SOC and PT
- Serious TEAEs by Primary SOC and PT
- Serious TEAEs Related to Study Drug by Primary SOC and PT
- Serious TEAEs Related to Study Drug by PT
- TEAEs by severity
- Injection Site Reactions (ISRs)
- ISRs by severity
- TEAEs leading to permanent treatment withdrawal by Primary SOC and PT
- TEAEs leading to study discontinuation by Primary SOC and PT
- Death due to TEAEs by Primary SOC and PT

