To evaluate the safety and tolerability of the anti-Bet v 1 monoclonal antibodies as compared to placebo following single administration (dose #1) and after repeat dosing (dose #2)	Incidence rates of treatment-emergent adverse events (TEAEs) and serious TEAEs through end of study
• To determine systemic concentrations over time of total antibody (free + antigen-bound) for each of the individual mAbs: REGN5713, REGN5714, and REGN5715 at various time points following single administration (dose #1) and after repeat dosing (dose #2)	Total REGN5713, REGN5714, REGN5715 concentration in serum over the duration of the study
To assess the immunogenicity of REGN5713, REGN5714, and REGN5715 in birch-allergic participants following single administration (dose #1) and after repeat dosing (dose #2)	• Incidences and titers of ADA to REGN5713, REGN5714, and REGN5715 over time

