10.4.5.1. Adverse Events

Definitions

For safety variables, 2 observation periods are defined:

- The pretreatment period is defined as the time from signing the ICF to before the first dose of study drug.
- The on-treatment period is defined as the day from first dose of study drug to the end of the study.

Treatment-emergent adverse events are defined as those that are not present at baseline or represent the exacerbation of a pre-existing condition during the on-treatment period and follow-up period.

Analysis

All adverse events reported in this study will be coded using the Medical Dictionary for Regulatory Activities (MedDRA®).

Summaries of all TEAEs by treatment group will include:

- The number (n) and percentage (%) of participants with at least 1 TEAE by system organic class (SOC) and preferred term (PT)
- TEAEs by severity (according to the grading scale outlined in Section 9.2.4), presented by SOC and PT
- Treatment-related TEAEs, presented by SOC and PT
- Treatment-emergent AESIs (which are defined in Section 9.1.4)
- Deaths, SAEs, and TEAE leading to permanent treatment discontinuation will be summarized by SOC and PT.

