- The change and percent change from pre-treatment and pre-season baseline in the symptom and medication scores (CSMS, TSS, TNSS, TOSS, and DMS), averaged during the BPS and peak BPS
- The mean of the total RQLQ(S) score during BPS and peak BPS
- Change and percent change from pre-treatment and pre-season baseline in the RQLQ(S) score during BPS and peak BPS

Drug Concentration, Safety and Immunogenicity (Part A and Part B)

- Incidence rates of treatment-emergent adverse events (TEAEs) and serious TEAEs through EOS
- Total REGN5713, REGN5714, and REGN5715 concentration in serum over the duration of the study
- Incidences and titers of ADA to REGN5713, REGN5714, and REGN5715 over time

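### SAP 10.1 specifies adverse event tables by study part and names no whole-period table, although the secondary safety endpoint is TEAE and serious TEAE incidence through end of study

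*SAP*

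**What the plan says.** SAP 7.1.2 lists among the secondary endpoints "Incidence rates of treatment-emergent adverse events (TEAEs) and serious TEAEs through EOS". Protocol 2.2 has the same endpoint, with end of study written out.

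Protocol 10.4.5.1 uses one post-dose period: "The on-treatment period is defined as the day from first dose of study drug to the end of the study". It then plans summaries of all TEAEs by treatment group and does not divide them by part.

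The introduction to SAP 10 takes the same view of time: "The time interval to detect any event or abnormality is during on-treatment period as defined in Section 10.1". SAP 10.1 defines that period as running from the first dose date to visit 15.

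SAP 10.1 then says "AEs will be summarized with incidence tables for Part A and Part B separately". The tables show numbers and percentages of participants, and "Multiple occurrences of the same event in a patient will only be counted once in the summary". The list that follows opens with "The following AE summaries will be presented for TEAEs" and has 16 entries. They include an overview, SOC/PT, severity, related, serious, AESI, injection site reaction, discontinuation and death tables. No entry is marked as by part or as whole-study.

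SAP 1.4 states that the protocol's key endpoints and statistical methods have not changed significantly, and its Table 1 has no entry on AE tabulation.

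**The concern.** A named secondary endpoint should have a table that reports it. A programmer who follows the one tabulation rule in SAP 10.1 would produce two sets of tables, one for each part. Neither set shows the share of an arm with at least one TEAE over the two-dose course.

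What is at stake is reporting. A reader with only the by-part tables would know the range in which the through-EOS incidence lies for each arm, but usually not its value. Where the ranges for two arms overlap, the tables alone do not settle how the arms compare over the whole study.

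**Working it through.** The plan gives no figure to reproduce here. The check compares the texts and then does the counting.

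**Texts side by side**

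| Source | Period covered | Split by part? |
|---|---|---|
| Protocol 2.2, SAP 7.1.2 (endpoint) | through end of study | no |
| Protocol 10.4.5.1 (planned summaries) | first dose to end of study | no |
| SAP 10, with the period defined in 10.1 | first dose to visit 15 | no |
| SAP 10.1 (tabulation rule) | Part A; Part B | yes |
| SAP 10.1 (list of 16 summaries) | not stated | not stated |
| SAP 1.4, Table 1 (changes) | no entry on AEs | no entry |

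Where the SAP wants a whole-study summary of other data, it says so. SAP 9.4 summarises procedures for the study total, and SAP 10.2 counts PCSVs at any time after randomization. AEs have no such wording.

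**Counting**

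Let n_A and n_B be the participants in an arm with at least one event in Part A and in Part B. Let n_AB be those with an event in both, and N the arm size, taken as common to both parts. The number with at least one event through EOS is

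n_A + n_B − n_AB,

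which lies between max(n_A, n_B) and min(N, n_A + n_B). By-part tables give n_A and n_B but not n_AB.

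Inputs: N = 300/4 = 75, from the approximate total in SAP 2.2. The event counts below are assumptions, because the documents give no expected TEAE rates by part. The last column supposes that events in the two parts are independent.

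| n_A, n_B (assumed) | Lowest | Highest | If independent |
|---|---|---|---|
| 15, 10 | 15 (20.0%) | 25 (33.3%) | 23.0 (30.7%) |
| 30, 25 | 30 (40.0%) | 55 (73.3%) | 45.0 (60.0%) |
| 45, 40 | 45 (60.0%) | 75 (100%) | 61.0 (81.3%) |
| 1, 1 | 1 (1.3%) | 2 (2.7%) | 2.0 (2.6%) |
| 1, 0 | 1 (1.3%) | 1 (1.3%) | 1.0 (1.3%) |

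For 30 and 25, independence gives n_AB = 30 × 25/75 = 10, hence 30 + 25 − 10 = 45.

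The range is wide for common events, narrow for rare ones, and zero when one part has no events. A participant can die or leave the study only once, so for those tables n_AB = 0 and the counts add exactly.

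**Denominator**

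The calculation takes one N for both parts. SAP 2.1 says some participants may not receive dose #2, and SAP 3.4 defines a single SAF with no Part B counterpart, so the Part B denominator is unstated. If it is smaller, by-part percentages are harder still to combine. A table from first dose to visit 15 on the SAF avoids the question.

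**The case against.** The strongest reply is that the SAP does not exclude an overall table. SAP 10.1 does not restrict AE tables to the by-part ones, and the list of TEAE summaries is introduced separately. Several places point to one period: the time-interval sentence in SAP 10, the single on-treatment definition in 10.1, the single SAF in 3.4, and the unsplit AE row in 14.1. On this reading the protocol summaries still stand, the by-part tables are additional, and Table 1 had nothing to record. By-part tables also have a purpose, since the safety objective in SAP 1.1.2 names both single administration and repeat dosing.

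Much of this stands. A reader might infer that the endpoint is produced by no planned table and cannot be derived. The documents do not support that. They are inconsistent rather than clearly silent, since protocol 10.4.5.1 and SAP 10 both set the whole period. AEs are collected to end of study and the SAP's final lock follows visit 15 (SAP 1.3), so participant-level data give the figure directly.

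A reader might also infer that arms with identical by-part tables could differ by 30 to 40 percentage points through EOS. That needs assumed incidences of 30% to 40% in each part, with complete overlap in one arm and none in the other. Nothing in the documents suggests such a pattern.

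The reply does not remove the mismatch. The time-interval sentence says which events count, which is compatible with then splitting them by part. The one explicit rule on how to tabulate AEs does not deliver the endpoint, and the reader has to infer a table that the SAP does not name.

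**Conclusion.** The point holds as an inconsistency to reconcile. SAP 10.1 specifies by-part AE tables and names no whole-period table, while the endpoint, protocol 10.4.5.1 and SAP 10 all cover first dose to end of study. Table 1 does not record the split as a change.

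The size depends on how common the event is. For common TEAEs and injection site reactions, two by-part counts can leave a wide range: 40.0% to 73.3% in the 30-and-25 illustration, which rests on assumed counts and a common denominator of 75. For rare serious TEAEs the gap is about one participant or none. For deaths and study discontinuations there is no gap in the counts.

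Safety is summarised descriptively and no hypothesis test depends on these tables. No data are lost and no efficacy conclusion changes. The consequence is limited to whether the endpoint is reported as defined.

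**What to change.** Amend the tabulation sentence in SAP 10.1. State that the listed TEAE summaries are presented on the SAF for the whole on-treatment period, first dose to visit 15, with each participant counted once across the two parts. At a minimum this should cover the overview, SOC/PT, severity, related, serious, AESI and injection site reaction tables. Identify the TEAE and serious TEAE tables as those that report the secondary endpoint in SAP 7.1.2. Keep the Part A and Part B tables as additional summaries, because they serve the dose #1 and dose #2 objective, and state the Part B denominator.

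The cost is a short change to the SAP text and one more run of tables already planned. No extra data are needed.

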• Study drug dosing (dose #2): Participants will be administered a SC dose of the study drug (dose #2 at visit 11) within approximately 3 weeks prior to the anticipated start of the natural BPS, intended as a single dose for coverage of the birch season. The goal dosing window is within 3 weeks prior to the anticipated start of the birch pollen season, at least 12 weeks after initial dose in Part A. The sponsor will define the last possible date for dosing in Part B in each geographical area based on the anticipated timing and duration of the local birch pollen season in consultation with the local pollen expert (eg, if season is expected to be ending soon based on consistently low birch pollen counts noted without any explanatory transient climactic condition such as rain/ cold weather, etc, then those participants may not receive dose #2). Participants who are

unable to receive dose #2 prior to the defined dosing end date will discontinue study drug (Section 7.3.2) but should be encouraged to remain in the study.

- Randomization and treatment assignment for Part B is discussed in Section 7.5.
 - Participants will be observed for 2 hours after study drug dosing and will be called by telephone (visit 12) approximately 1 day after dosing to assess for any potential adverse events.
- Follow-up period: after the end of the birch pollen season for approximately 4 weeks.

Part B will be an approximately 18-week period based on timing and length of the natural BPS including an approximate 4-week safety follow up after the end of the season.

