7.3.2. Study Drug Discontinuation

Participants who permanently discontinue from study drug should be encouraged to remain in the study. Those who agree and do not withdraw from the study will be asked to return to the clinic for all remaining study visits per the visit schedule.

Participants who permanently discontinue from study drug and who opt to withdraw from the study will be asked to complete study assessments, per Section 8.1.2.

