- At minimum, a 12-week interval between doses #1 and #2 is required. Dose #2 is intended to be given within 3 weeks prior to an anticipated birch season and a dosing stop date is defined within approximately 1 week after the concurrent birch pollen season start. Some participants may receive dose #2 after start of the birch pollen season. Some participants that are enrolled later in the study may not receive dose #2 if they do not meet the minimum 12-week interval prior to the defined dosing stop date.
- In-season peak EEU challenge at visit 13 is intended to be conducted in the birch season during the approximate anticipated peak season (after dose #2 for those expected to receive it)
- End-of-season EEU challenge (visit 14) is expected to be performed after the end of the local birch season. (Note: Participants that are highly symptomatic to grass pollens or unable to wash out allergy rescue medications may not perform this EEU challenge.)

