3.4. The Safety Analysis Set (SAF)

The safety analysis will be based on the safety analysis set (SAF), defined as all randomized participants who receive any study drug, regardless of the amount of treatment administered. The SAF is based on the treatment received (as treated). As-treated is defined as when a patient receives at least one dose of any amount of study drug, in case of interrupted dosing. The patient will be regarded as treated with 3-mAb cocktail study drug REGN5713-5714-5715 if the patient receives at least 1 dose of the 3-mAb cocktail. Similarly, if a patient receives at least one dose of the 2-mAb cocktail, but no doses of REGN5714, the patient will be considered treated with REGN5713-5715. If a patient receives at least one dose of the single mAb REGN5715 but no doses of REGN5713 or REGN5714, then the patient will be considered treated with REGN5715. If the patient receives no REGN5713, REGN5714, or REGN5715, the patient is considered as treated with placebo.

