3.6. Pharmacokinetic Analysis Set (PKAS)

The PK analysis set (PKAS) includes all participants who received any active drug and who had a at least 1 non-missing serum drug concentration following a single dose of study drug. Participants will be analyzed according to the treatment actually received rather than as randomized.

GENERAL STATISTICAL ANALYSIS CONSIDERATIONS 4.

Unless otherwise stated, the following conventions will be applied when presenting summary level statistics for data.

Date: May 31, 2023

Continuous variables will be summarized within each treatment group, presenting the following summary statistics. The sample size (i.e. number of observations with an available value of the variable), average, sample standard deviation, median, minimum, maximum, 1st quartile and 3rd quartile.

Categorical data will be summarized within each treatment group by frequency (i.e., total number of observations within each level of the categorical variable in a given treatment group). All levels of the categorical variable will be included. If there are observations where the level of the categorical variable is missing, a separate category titled "Missing" will be created. For categorical variables that are ordinal in nature, the order in which the levels of the categories are displayed will be consistent with the natural ordering of the category levels. Percentages will also be calculated for each level of the categorical variables with respect to the total sample size for the respective treatment arm.

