In addition, some in-season efficacy analyses in Part B may be performed including participants with available in-season data irrespective of whether they received dose 2.

More details concerning other secondary endpoints, see Section 14.1.

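### The Part B adverse-event tables have no dose-#2 denominator or start date, so their rates may be taken over people who were never re-dosed

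*SAP*

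**What the plan says.** SAP 1.1.2 and Protocol 2.2 make safety against placebo a secondary objective, both after dose #1 and after repeat dosing. The matching endpoint is the incidence of TEAEs and serious TEAEs through end of study.

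On presentation, SAP 10.1 says "AEs will be summarized with incidence tables for Part A and Part B separately". Its list of tables includes AESIs and injection-site reactions. On population, SAP 10 says "The analysis of safety will be performed on the SAF", and SAP 3.4 has that set "defined as all randomized participants who receive any study drug, regardless of the amount of treatment administered". The summary table in SAP 14.1 gives the SAF for adverse events and plans no other analysis. SAP 4 sets a general convention, to apply unless otherwise stated: "Percentages will also be calculated for each level of the categorical variables with respect to the total sample size for the respective treatment arm".

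SAP 10.1 defines one on-treatment period, from first dose to visit 15, and judges treatment emergence against the state before randomization. Nothing resets at dose #2.

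Not everyone will be re-dosed. SAP 2.1 says "Some participants that are enrolled later in the study may not receive dose #2". Under Protocol 5.1 those who miss the dosing end date "will discontinue study drug (Section 7.3.2) but should be encouraged to remain in the study", and under Protocol 7.3.2 they "will be asked to return to the clinic for all remaining study visits per the visit schedule". SAP 7.2.2 allows some Part B efficacy analyses to include "participants with available in-season data irrespective of whether they received dose 2". For efficacy, SAP 3.1 defines a set of people dosed in Part B (FAS-B). Safety has no counterpart.

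**The concern.** Protocol 3.3 reports that the 3-mAb cocktail has been given to 229 people in completed studies, each as a single dose. It names systemic hypersensitivity and immunogenicity as the important potential risks. Reactions to a second injection are therefore the new safety information in this trial, and the Part B tables are where a reader will look for them.

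If those tables use the SAF, people who never received dose #2 sit in the denominator. They cannot have a dose-#2 reaction, so that rate is pulled down. They can have other in-season events, and these would be counted together with those of re-dosed people.

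**Working it through.** The plan gives no figure on this point, so the check starts from the text.

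**1. Can some SAF members be barred from dose #2?** SAP 2.1 requires at least 12 weeks (84 days) between doses and sets the dosing stop within about 1 week (7 days) after local season start.
- Cut-off: 84 − 7 = 77. Anyone given dose #1 fewer than about 77 days before local season start cannot be re-dosed.
- SAP 7.2.1.1 states that for some randomized participants the season began too early for the day 29 challenge. The visit window is ±7 days, so the latest such case is at day 29 + 7 = 36 at season start and day 36 + 7 = 43 at the stop date.
- With the 14-day illness extension (footnote 9 to the Schedule of Events): day 50 + 7 = 57.
- Counting dose #1 as day 1, the earliest day for dose #2 is 1 + 84 = 85. Both 43 and 57 fall short.

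So the never re-dosed group is not empty. Those of them who received dose #1 are in the SAF and are asked to keep attending.

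**2. Does another rule set the Part B denominator or start?**
- Protocol 10.4.5.3 and SAP 9.1 tie observation time in each part to that part's dose, but only for exposure and duration.
- SAP 11.4 cuts Part A from Part B at the later of the last out-of-season EEU visit and visit 10. It governs visit mapping, and its window table has no adverse-event column. If it were applied to AEs, Part B would nominally open at day 127 and run to day 253 (126 days), with dose #2 at day 155. The first 155 − 127 = 28 days, or 28/126 = 22%, would precede dose #2.
- AE start-date imputation in SAP 11.3 is anchored to the first dose only.

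**3. What would the SAF denominator do?** Let s be the re-dosed share. The documents do not give s or any event rate, so all values here are assumptions. N = 300/4 = 75 per arm.

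Dose-#2 reactions: rate shown = s × true rate.

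| | s = 0.9 | s = 0.8 | s = 0.7 |
|---|---|---|---|
| True rate 2% | 1.8% | 1.6% | 1.4% |
| True rate 10% | 9% | 8% | 7% |
| Difference 2.0 − 0.5 = 1.5 points | 1.35 | 1.20 | 1.05 |
| Ratio 2.0/0.5 | 4 | 4 | 4 |
| Expected events at 2% (75 × s × 0.02) | 1.35 | 1.2 | 1.05 |

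Overall Part B TEAEs: rate shown = s × r1 + (1 − s) × r0, where r1 = 30% in re-dosed and r0 is the rate in never re-dosed people.
- r0 = 20%: 29%, 28%, 27%.
- r0 = 40%: 31%, 32%, 33%.

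The bias in overall TEAEs can therefore go either way.

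Zero AESIs observed: one-sided 95% upper bound = 1 − 0.05^(1/n).
- All 75 in the denominator: 3.9%.
- 68, 60 or 52 re-dosed (90%, 80%, 70%, in whole people): 4.3%, 4.9%, 5.6%.

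**The case against.** The strongest reply is that no sentence fixes the Part B denominator. The SAP 4 convention holds unless otherwise stated, and elsewhere both documents tie Part B observation to its own dose. A programmer might well divide by the re-dosed number. This stands in part. A reader might infer that the plan commits to diluted dose-#2 rates, and the documents do not support that: dilution follows from reading SAP 10, 3.4 and 4 together. What they do support is that the only stated population is the SAF and that nothing in SAP 10.1 departs from it.

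Second, the endpoint runs through end of study, and the SAF with a single on-treatment period fits it. That is right, and that summary is not in question. But the objective names dose #2, and the Part B tables are the only planned AE display for it.

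Third, people never re-dosed still carry drug. With half-lives of 26.9 to 35.1 days (Protocol 3.2.2), simple decay leaves 2^(−84/26.9) = 11% to 2^(−84/35.1) = 19% of dose #1 at 84 days. That is a reason to report their in-season events, but not to count them as exposed to dose #2.

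Fourth, safety is descriptive and counts will be small. SAP 5.2 and 9.1 will show how many were re-dosed, so counts of dose-#2 reactions can be re-divided. This stands, and it limits the size. It does not work for overall, serious or related TEAEs, where the two groups share one row.

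**Conclusion.** The point holds as a gap with a likely consequence. SAP 10.1 gives the Part B tables no denominator and no start. The stated SAF rule, applied to them, would include people who cannot have received dose #2, and the nearest part cut opens before dose #2.

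The effect is small to moderate. It scales with the re-dosed share, which the documents do not give, and dilution is nil if everyone is re-dosed. The illustrative figures rest on assumed shares of 70% to 90% and assumed event rates. A reader might also infer that the comparison with placebo is distorted. For dose-#2 reactions the ratio is kept if shares are similar across arms; only the absolute rates and differences shrink. The primary result, type I error and the whole-study TEAE endpoint are unaffected. The change should be made because the second exposure is the new safety information and the correction is cheap.

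**What to change.** - **SAP 3.4:** add a Part B safety set of SAF participants who received dose #2, as treated. Use it for the Part B AE, AESI and injection-site tables.
- **SAP 10.1:** start the Part B AE period at the date and time of dose #2. Count as Part B events those that are new or worsened relative to the state before dose #2. Assign events before dose #2, and all events in participants never re-dosed, to the dose-#1 period. Show the in-season events of the never re-dosed in a separate column with their own N.
- **SAP 11.3:** add a dose-#2 anchor to the AE start-date imputation, so that a partly dated reaction to dose #2 does not fall outside Part B.
- **Main summary:** list explicitly a first-dose-to-end-of-study table on the SAF.

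The cost is SAP wording and programming: one set, one period with its own reference state, one imputation rule and one column. Dosing and AE dates are already collected, and no event leaves the overall table. The downside is selection. Protocol 7.3.2.1 stops dosing after serious or severe allergic reactions related to study drug, so the dose-#2 set consists of people who tolerated dose #1. It supplements the SAF table and does not replace it.
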